
Potential Study Benefits

This study will provide no direct benefit to individual participants. However, the knowledge gained may hopefully help guide future treatments in depression and may help advance the field of psychiatry as a whole.

Alternatives to Participation (optional)

The alternative to participation is to not participate.

Data and Safety Monitoring

The PI will monitor the study for any serious and adverse events. All serious events (SAE) will be reported to the IRB: a) Death immediately b) Life-threatening and all other SAEs within 7 calendar days. Should there be a serious event that occurs that increases the risks to the participants the study will be stopped, an investigation will be conducted, and a findings report will be generated before the study is resumed. Detailed Data Safety Monitoring Plan: This section describes the Data and Safety Monitoring Plan and quality assurance (QA) procedures that will be used for this proposed study. This monitoring plan details the frequency of monitoring visits, regulatory document review, and compliance review. Monitor Selection: One monitor will be assigned for this study and will be responsible to complete the monitoring process. The monitor will be a research coordinator at the center who is not the lead research coordinator for this study. An updated CV will be kept on file in the Research Personnel regulatory binder to document the qualifications of the monitor. Data Management: All data will be deidentified and only qualified research personnel will be have access. Records will be kept electronically on password protected servers. Safety Monitoring: All unanticipated problems will be reported to the Principal Investigator or delegated research staff for the duration of the study. The Principal Investigator has the front-line responsibility for identifying potential adverse events experienced by study participants, making adjustments accordingly, and reporting the experience. The P.I. is responsible for tracking these reports and relaying them as required to the IRBs and other investigators. Data integrity, safety, and privacy will be monitored by the PI and the coordinators. The following activities will be completed by the monitor to close out the study: Ensure all data has been reviewed and collected; Confirm all reports of unanticipated problems have been reported to the IRB(s); Review the regulatory documentation and subject files for completeness and compliance with all applicable federal regulations; Ensure that all continuing review reports were submitted to and approved by the IRB(s) Review requirements for record retention with the investigator and the clinical staff. The checklist will be signed by the monitor and included in the regulatory files.

The following documents are currently attached to this item:

There are no documents attached for this item.

Risk / Benefit Assessment

This study is minimal risk. There is essentially zero risk of harm from the research procedures (MRI, TMS, assessments of symptoms). The potential benefit to society through the increased understanding of treatment methods in MDD/PTSD far outweighs the potential risk from the MRI and TMS procedures. Additionally, those who would be unable to tolerate TMS or an MRI scan will be screened out.

General Attachments

The following documents are currently attached to this item:

[Cover Letter \(2020.12.09_coverletter_825761.doc\)](#)

[Informed consent form \(2020.12.09_icf.v10_clean_825761.docx\)](#)

[Informed consent form \(2020.12.09_icf.v10_tracked_825761.docx\)](#)

[Additional forms \(2020.12.09_irbcorr_reenrolledpt_825761.pdf\)](#)

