There are no documents attached for this item.

Department budget code

None

Multi-Center Research

Penn as lead

1. Is this a multi-center study where Penn is serving as the Lead Site or the Penn PI is serving as the Lead Investigator?

No

Management of Information for Multi-Center Research**Penn irb of record**

2. Is this a multi-center study where the Penn IRB will be asked to serve as the IRB of Record for other external study sites?

No

Other Sites

No other sites

Protocol

Abstract

Non-invasive transcranial magnetic stimulation (TMS) is now FDA-approved for the treatment of major depressive disorder (MDD). However, there is growing evidence that the targeting strategy for

delivering TMS treatment would yield superior clinical outcomes if it were more tailored to individual neuroanatomy. In this study, we plan to examine whether functional MRI-guided TMS might be effective at temporarily influencing neural circuit communication. If this is true, future studies may utilize these methods to yield an even greater leap forward in promoting optimal clinical outcomes using full doses of TMS for treatment.

Objectives

Overall objectives

We aim to establish the efficacy of TMS stimulation at probing and temporarily influencing brain activity using targets defined by resting connectivity in MDD patients. We hypothesize that fMRI-guided TMS will be effective in modulating the connectivity of neural circuits.

Primary outcome variable(s)

Functional brain activity due to TMS performed at an fMRI-guided brain target

Secondary outcome variable(s)

Changes in functional brain activity after the 3 day stimulation regimen

Background

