The subgenual Anterior Cingulate Cortex (sgACC) has been well established as a brain area sensitive to negative mood inductions and is implicated in neural abnormalities associated with affective and stress disorders. It is therefore one of the primary targets for deep brain stimulation (DBS) treatment of MDD using surgically implanted DBS devices. Recent posthoc imaging studies of patients who have undergone TMS treatment for depression suggest that treatment outcomes tended to be better when patients were by chance stimulated in an area of lateral prefrontal cortex that had high levels of functional connectivity with sgACC. Based on this finding, and on our own interleaved TMS/fMRI probe data, we contend that targeting delivery of TMS to the brain surface non-invasively as indicated by sgACC resting functional connectivity may be especially effective in downregulating sgACC and thereby producing superior clinical outcomes. We have used TMS/fMRI to better understand causal communication among circuits typically examined with resting fMRI alone (Chen et al., 2013). Our recent work suggests there are specific sites that, when stimulated, influence subcortical brain areas implicated in affective disorders such as the sgACC. Previously, we targeted TMS based on brain atlases mapped onto individual brain surfaces. This study will utilize individualized targeting from participants' own fMRI scans. We will focus on a target region of the lateral prefrontal cortex (LPFC) that our data suggest is particularly effective at influencing the sgACC. As alternative brain targets, we will also test the efficacy of prefrontal sites with hypothesized connections to downstream depression-related abnormalities. A normal, FDA-approved clinical application of TMS involves long trains of repetitive TMS applied for approximately 40 minutes, 5 days/week, over 2-6 weeks, for a total of 10-30 TMS visits. The present study utilizes the same FDA-approved devices (Magventure Cool-Coil B65, MagVenture X100 Stimulator) to administer TMS. We will be administering brain stimulation in smaller doses as compared with the FDA-approved protocol, but using a well-validated protocol, theta-burst stimulation (Huang et al., 2005), which will result in a reduced number of total pulses delivered to the subject in any given TMS session. This is not a treatment study, and stimulation is not designed to provide treatment in this study. Instead, the TMS delivery is meant to temporarily modify brain circuit communication between the lateral prefrontal cortex and subcortical structures to prove that this pathway can be influenced non-invasively with TMS. In addition to these repetitive TMS protocols, we will perform brief TMS delivery in the MRI machine with a research device (MRI-B91 Air Cooled Coil). We have attached several additional examples of prior studies which have safely utilized TMS outside of its FDA-approved protocol, even in heightened doses. For instance, in prior studies subjects have received the FDA-approved 3000 rTMS pulses, but done bilaterally instead of unilaterally (6000 total stimulations) every weekday over 4-6 weeks (see Bakker et al., 2015). Similarly, subjects have received 3600 rTMS pulses every weekday over 10 days (see Chistyakov et al., 2015), or 3000 rTMS pulses every weekday over 6 weeks (see O'Reardon et al., 2007). Another study applied the FDA-approved protocol in more than a double-dose, with 6800 stimulations to 1 site every weekday over 7 weeks average participation (Hadley et al., 2013). The present study utilizes many fewer stimulations than these other protocols, with each visit including a maximum of 3700 pulses. For additional information, please see Anderson et al., 2006 for demonstrations of the safety of repeated exposure to TMS. Likewise, please see Wagner et al., 2007 and Parkin et al., 2015 for reviews of the importance of TMS research and how our proposed studies fit in the present and growing body of literature.

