
The following documents are currently attached to this item:

There are no documents attached for this item.

Deception

Does your project use deception?

No

International Research

Are you conducting research outside of the United States?

No

Analysis Plan

Clinical outcome will be evaluated on symptom scales in a TMS target x Time ANOVA. Similarly, rate of change (slope) x TMS Target will indicate how rapidly each round of stimulation influences symptoms.

The following documents are currently attached to this item:

There are no documents attached for this item.

Data confidentiality

- Paper-based records will be kept in a secure location and only be accessible to personnel involved in the study.**
- Computer-based files will only be made available to personnel involved in the study through the use of access privileges and passwords.**
Prior to access to any study-related information, personnel will be required to sign statements agreeing to protect the security and confidentiality of identifiable information.
- Wherever feasible, identifiers will be removed from study-related information.**
A Certificate of Confidentiality will be obtained, because the research could place the subject at risk of criminal or civil liability or cause damage to the subject's financial standing, employability, or liability.
- A waiver of documentation of consent is being requested, because the only link between the subject and the study would be the consent document and the primary risk is a breach of confidentiality. (This is not an option for FDA-regulated research.)**
- Precautions are in place to ensure the data is secure by using passwords and encryption, because the research involves web-based surveys.**
Audio and/or video recordings will be transcribed and then destroyed to eliminate audible identification of subjects.

Subject Confidentiality

Patients entering the study will be given a unique identifying code. This code will be used on all data obtained from scans or the medical record. Everything will be immediately coded and this coded information will be stored in secure cabinets inside locked rooms or in password protected, IRB compliant online databases, such as REDCap. Any documents connecting the code with the participant name will also be stored in secure cabinets inside locked rooms or in password protected, IRB compliant online databases, such as REDCap.

Sensitive Research Information*

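### Both listed outcomes are functional brain activity, but the Analysis Plan tests only symptom scales, through a TMS target factor whose levels are never defined

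*Combined protocol and SAP*

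**What the plan says.** **Outcomes and hypothesis (Objectives).** The primary outcome is "Functional brain activity due to TMS performed at an fMRI-guided brain target". The secondary outcome is "Changes in functional brain activity after the 3 day stimulation regimen". The stated hypothesis is: "We hypothesize that fMRI-guided TMS will be effective in modulating the connectivity of neural circuits".

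**Analysis (Analysis Plan).** The section has two sentences, and the form records no document attached to it. The first is "Clinical outcome will be evaluated on symptom scales in a TMS target x Time ANOVA". The second says that "rate of change (slope) x TMS Target will indicate how rapidly each round of stimulation influences symptoms". No symptom scale is named.

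**Purpose (Background).** "This is not a treatment study, and stimulation is not designed to provide treatment in this study".

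**Target.** The Background says "We will focus on a target region of the lateral prefrontal cortex (LPFC) that our data suggest is particularly effective at influencing the sgACC", and adds that other prefrontal sites will be tested as alternative targets. The Design gives every participant active stimulation by the same fMRI-guided method. The visit schedule describes Visits 4 to 6 as stimulation of the guided site, in the singular, and the compensation schedule repeats this.

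**Scans (Study Design and Procedures).** Combined TMS/fMRI scans take place at Visit 3, before the three stimulation days, and at Visit 7, after them. Resting-state fMRI is named only at Visit 2, where it is used to set the targets.

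**The concern.** The outcomes and the analysis do not meet. The study is built around two TMS/fMRI scans, and its outcomes and hypothesis depend on them, yet nothing in the document says how those scans will be analysed. The analysis that is described concerns a quantity that is not an outcome.

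Two things are at stake. First, someone following the plan would finish the study without testing the primary outcome, the secondary outcome or the hypothesis. If the imaging analysis is instead chosen once the outcome scans have been seen, the region, the contrast and the type of measure (evoked response or connectivity) are all open, and the false-positive rate is not controlled. Second, the symptom analysis cannot be carried out as specified. It rests on interactions with a target factor that has either a single level or an undefined set of levels.

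**Working it through.** **Plan's own figure.** Accrual gives 40 completers with usable data and about 55 screen failures, losses, withdrawals or unusable completers: 40 + 55 = 95, which matches the stated ceiling. The text says this number is needed to test the hypotheses, but no test of the stated hypothesis follows.

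**Step 1: match outcomes to analyses.**

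| Item | Quantity | Analysis given? |
|---|---|---|
| Primary outcome | Brain activity due to TMS | None |
| Secondary outcome | Change in brain activity after 3 days | None |
| Hypothesis | Circuit connectivity | None |
| Analysis Plan, sentence 1 | Symptom scales, target by Time | Yes, but not a listed outcome |
| Analysis Plan, sentence 2 | Symptom slope by target | Yes, but not a listed outcome |

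So 0 of 2 outcomes have an analysis, and 2 of 2 analysis sentences address something unlisted. The before/after comparison of Visits 3 and 7 can be inferred for the secondary outcome. The measure, region, contrast, model, test and multiplicity rule cannot be inferred for either outcome.

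**Step 2: degrees of freedom of the interaction.** With k target levels and T symptom occasions, df = (k − 1)(T − 1). The documents give neither k nor T for symptoms. T = 2 would be Visits 3 and 7. T = 5 would be Visits 3 to 7; this is an assumption, because the Procedures promise only brief assessments at Visits 4 to 6 and do not call them symptom scales.

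- k = 1, T = 2: (0)(1) = 0
- k = 1, T = 5: (0)(4) = 0
- k = 2, T = 2: (1)(1) = 1
- k = 2, T = 5: (1)(4) = 4

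A rank check for 40 participants agrees. The models are Time only; Time plus target; and Time, target and their interaction.

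- k = 1: ranks 2, 2, 2 for T = 2 and 5, 5, 5 for T = 5. Target and its interaction add nothing, but the Time columns keep their full rank.
- k = 2: ranks 2, 3, 4 for T = 2 and 5, 6, 10 for T = 5. The interaction can be estimated.

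The slope-by-target term behaves the same way: with k = 1 there is no second slope to compare, and only the mean slope remains.

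**Step 3: illustration of an open choice of region.** The conclusion does not depend on this. Assume 5 or 10 candidate regions, each tested at 0.05 without correction. If independent, the chance of at least one false positive is 1 − 0.95^5 = 0.226 or 1 − 0.95^10 = 0.401. With pairwise correlation 0.5 (simulated), it is about 0.18 or 0.29.

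**The case against.** **The imaging analysis is obvious from the design.** In part. The scans and the before/after comparison can be inferred, and the Background names the pathway from lateral prefrontal cortex to sgACC. But it also mentions subcortical structures generally and other prefrontal sites, and it does not turn the pathway into a measure or a test. Resting-state data are named only at Visit 2, so it is unclear whether the scheduled outcome scans could support a connectivity test.

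**This is an ethics-board form, not a full analysis plan.** Brevity alone would be a fair defence. But the Analysis Plan section was filled in, and with an analysis of something else.

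**There may be several targets.** This stands as a possibility. A singular site at Visits 4 to 6 can mean one site per participant, differing between participants, and one targeting method is not necessarily one target. The Background's alternative targets are the clearest sign of more than one. Other plurals are weak evidence: "using targets defined by resting connectivity in MDD patients" fits one target for each of many patients. A reader might infer that the factor certainly has one level; the documents suggest this but do not establish it. Nor do they say how many levels there are, who receives which, or whether target varies within or between participants.

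**With one target the symptom analysis does not vanish.** Correct. The Time effect and mean slope remain estimable; only the target terms and their interactions are lost.

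**Conclusion.** The point holds and needs correcting before the outcome scans are analysed. Neither of the two listed outcomes, nor the connectivity hypothesis, has an analysis; both analysis sentences test symptoms, which are not listed outcomes. This follows from the text alone and needs no assumption about effect size or power.

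The second part is conditional. On the most natural reading of the Design, with one target level, both interactions have 0 df and only Time and mean slope can be estimated. With more than one level the interactions exist, but they cannot be reproduced because the levels and their assignment are not stated.

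Two stronger readings are not supported. A reader might infer that no imaging analysis plan exists anywhere. The documents show only that none is attached to the Analysis Plan item; the general attachment list omits items that the text says are attached, so it is not a full inventory. A reader might also infer from the May 2018 protocol reference and the December 2020 attachment dates that scans had already been analysed. The dates do not show this.

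**What to change.** Before the Visit 3 and Visit 7 outcome scans are analysed (Visit 2 imaging has to be analysed to set targets), rewrite the Analysis Plan as follows.

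1. **Primary.** Name one predefined imaging measure, with region, contrast and test. The choice is the investigators'. One example is the TMS-evoked sgACC response at Visit 3 under guided lateral prefrontal stimulation, with a one-sample two-sided 0.05 test. Use a connectivity measure, which is closer to the hypothesis, only if the scheduled scans acquire it at both visits.
2. **Secondary.** Analyse the within-person Visit 7 minus Visit 3 change in the same measure.
3. **Exploratory.** Label symptom scales and other regions as exploratory, with multiplicity control across regions.
4. **Target factor.** If there is one target, replace the two interactions with tests of Time and mean slope. If there are more, reconcile the Background, Design and Analysis Plan by stating the levels and how they are assigned.
5. **Date.** Date the revision and say which outcome scans, if any, had already been analysed.

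**Cost.** With one target and an evoked-response measure, only the Analysis Plan wording changes and the scheduled scans are used. With several targets the Design text must change too. The investigators give up the freedom to choose region and contrast later. A single-group test still cannot separate a circuit-specific effect from non-specific effects of stimulation, and the plan should say so.

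### The primary imaging outcome names no response region, contrast, scan or direction, and no imaging test is planned, so the primary region could be chosen after the data are seen

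*Combined protocol and SAP*

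**What the plan says.** All references are to the combined protocol and SAP.

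- **Objectives, primary outcome.** The complete definition is "Functional brain activity due to TMS performed at an fMRI-guided brain target".
- **Objectives, secondary outcome.** "Changes in functional brain activity after the 3 day stimulation regimen". This adds a before/after comparison but again no region or sign.
- **Objectives, overall.** "We hypothesize that fMRI-guided TMS will be effective in modulating the connectivity of neural circuits". The hypothesis concerns connectivity, whereas both outcomes concern activity. It names no circuit and gives no direction.
- **Background, rationale.** Targeting by sgACC resting connectivity "may be especially effective in downregulating sgACC and thereby producing superior clinical outcomes". On the main target: "We will focus on a target region of the lateral prefrontal cortex (LPFC) that our data suggest is particularly effective at influencing the sgACC".
- **Background, wider aims.** "As alternative brain targets, we will also test the efficacy of prefrontal sites with hypothesized connections to downstream depression-related abnormalities". On the purpose of stimulation in this study: "the TMS delivery is meant to temporarily modify brain circuit communication between the lateral prefrontal cortex and subcortical structures".
- **Analysis Plan.** "Clinical outcome will be evaluated on symptom scales in a TMS target x Time ANOVA", followed by one sentence on the slope of symptom change. It contains no imaging test, region of interest, sidedness or multiplicity rule.
- **Accrual.** 40 participants with usable data, about 55 losses, and enrolment of up to 95.
- **Study duration and Procedures.** There are two TMS/fMRI scans, at Visit 3 (before the three theta-burst sessions) and at Visit 7 (after them).

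**The concern.** A primary outcome should fix, before the data are seen, which number will be tested. Here four choices are open: the region, the contrast or baseline, the scan, and the direction. TMS with concurrent fMRI produces a response map over the whole brain, so leaving the region open gives many candidate results for one claim.

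Two things are at stake. If the region is chosen after inspection and tested at an ordinary significance level, the false-positive rate is no longer the nominal one. If the search is corrected instead, power falls in a study of only 40 usable participants. The Background already identifies a region and a sign, so the plan pays one of these prices without need. The study also sets out to prove that a pathway can be influenced, and justifies its enrolment by the need to test its hypotheses adequately. Both call for a defined test.

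**Working it through.** **1. Is the missing detail supplied elsewhere?**

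| Element | Objectives | Background | Analysis Plan |
|---|---|---|---|
| Response region | none | sgACC; also subcortical structures in general and unnamed downstream abnormalities | none |
| Contrast or baseline | none | none | none |
| Scan | none for the primary outcome | none | none |
| Direction | none | downregulation of the sgACC, as a contention; none in the statement of this study's purpose | none |
| Measure | activity (outcomes), connectivity (hypothesis) | both | symptom scales |

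The sgACC is the only downstream region named anywhere, and the only one given a direction. No section carries it into the outcome definition or into a test.

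**2. The plan's own figure.** 40 usable + 55 lost = 95, which reproduces the enrolment ceiling. The 40 itself cannot be reproduced, because the documents give no alpha, sidedness, power, effect size or standard deviation.

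**3. Power cost of a corrected search (illustrative).** From the documents: n = 40. Assumed: a one-sample or paired t-test, two-sided alpha 0.05, 80% power, and R candidate regions with Bonferroni correction. The detectable standardised effect d solves

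P(T > t[1 − 0.05/(2R), 39]) = 0.80, where T is noncentral t with 39 degrees of freedom and noncentrality d × √40.

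| R | Alpha per region | Critical t | Detectable d |
|---|---|---|---|
| 1 | 0.05 | 2.02 | 0.454 |
| 10 | 0.005 | 2.98 | 0.608 |
| 100 | 0.0005 | 3.80 | 0.741 |

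Put the other way, a true effect of 0.454 has 80% power in one named region, but 47% when corrected over 10 regions and 20% over 100.

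**4. False-positive cost of an uncorrected search (illustrative).** With independent regions, the chance of at least one false positive is 1 − 0.95^R:

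- R = 5: 1 − 0.95^5 = 22.6%
- R = 10: 1 − 0.95^10 = 40.1%
- R = 100: 1 − 0.95^100 = 99.4%

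Brain regions are correlated, which lowers these figures. Assuming one common correlation between all regions:

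| Common correlation | 10 regions | 100 regions |
|---|---|---|
| 0 | 40% | 99% |
| 0.3 | 35% | 94% |
| 0.5 | 29% | 78% |
| 0.7 | 21% | 50% |

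Even at a correlation of 0.7 with 10 regions, the rate is about four times the nominal 5%.

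**The case against.** **No success rule exists.** A reader might infer that a change anywhere in the brain would count as success. The documents do not say so: they define no threshold, test or success criterion for imaging. The outcome is unspecified, which is not the same as a whole-brain, two-directional rule. What stands is that nothing in the plan prevents selection of the region afterwards.

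**Direction.** A reader might also infer that a rise in sgACC activity would contradict the study's hypothesis. It would contradict the Background rationale, but not the hypothesis as written, which speaks only of modulation. The downregulation sentence is a contention tied to clinical benefit. The Background then says that this is not a treatment study and gives its purpose without a sign. Making a decrease the condition for success would therefore narrow the sponsor's hypothesis. This objection stands, and the fix allows for it.

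**Wider aims.** The Background also mentions alternative prefrontal targets, whose downstream regions need not include the sgACC. That is correct, and the sponsor may prefer more than one primary region. But these aims widen the choice without listing the regions, which is a reason to list them.

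**Hypothetical numbers.** The region counts are assumed, and no uncorrected or Bonferroni search is planned. The figures for independent regions are upper bounds. They show what an open choice could cost, not what this study will do.

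**Overlap with the missing imaging analysis.** Multiplicity and sidedness would normally be settled there, so the overlap is real. Even so, an imaging model could be added and the primary result would remain undefined until region, contrast, scan and sign reporting are fixed.

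**Conclusion.** The point holds as a gap in the definition of the primary outcome. Region, contrast, scan and direction are all absent, no imaging test is planned, and the region could be chosen after the data are seen. The Background makes the sgACC the natural choice and expects downregulation, but the documents do not support saying that any activity would be declared a success, or that an increase would refute the stated hypothesis.

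Its size can only be illustrated. With 40 participants and 80% power, the detectable effect is 0.45 for one region against 0.61 (10 regions) or 0.74 (100 regions). The uncorrected false-positive chance is at most 40% or 99%, and about 21-35% or 50-94% at common correlations of 0.7 to 0.3. Only the 40 comes from the documents; alpha, power, region counts and correlations are assumptions. That the outcome is undefined depends on none of them. The change should be made before the imaging data are analysed.

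**What to change.** State one primary test in the Objectives and repeat it in the Analysis Plan:

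- **Primary.** Mean TMS-evoked response in a pre-drawn sgACC region at Visit 3, for stimulation at the fMRI-guided lateral prefrontal site, against a stated within-scan baseline, tested two-sided at 0.05.
- **Sign.** Report it whatever it is. Describe the result as support for the downregulation rationale only if it is a decrease. An increase may be reported as influence on the pathway, but not as support for that rationale.
- **Secondary.** Visit 7 minus Visit 3 change in the same measure, at the same site and against the same baseline.
- **Exploratory.** All other regions and the alternative stimulation sites, with whole-brain correction.
- **Wording.** Reconcile the hypothesis, which concerns connectivity, with the outcomes, which concern activity.

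Visit 3 suits a test of the evoked response because it precedes the theta-burst sessions, but the text does not dictate it. If the sponsor prefers another scan or a connectivity measure, that is acceptable provided that it is fixed in advance.

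The cost is a few sentences, with no extra scans or participants. The downside is that findings outside the sgACC become exploratory.
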